2.3 Efficacy Outcomes

2.3.1 Primary Outcome

The proportion of patients with a physiologically optimal result post PCI ($\text{FFR} \geq 0.90$). The primary outcome will be summarised in the FAS as a whole and by treatment group. A test and 95% CI for 2 proportions (adjusted Wald method) will be employed, together Fisher's exact test.

Additional secondary analyses on this outcome will use logistic regression to investigate whether any of the baseline characteristics affect the outcome. Given the sample size of 130 per group and the large number of baseline characteristics (since logistic regression is a large sample method), this will be performed by first investigating each characteristic on its own (together with the treatment group). Any variables that are significant here will be added to build a larger model, bearing in mind sample size limitations.

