- E. At the end of the procedure the pressure wire sensor will be withdrawn to the tip of the guiding catheter and compared with the aortic pressure. A pressure drift of ≤ 0.03 will be accepted and the final FFR result adjusted accordingly.
- F. If there is a drift of ≥ 0.04 , the wire should be re-equalised and the final FFR measurement be repeated.
- G. The patients will have their demographics and procedure details recorded. All patients will receive 3-month telephone follow-up.

Group 2 (Control Group):

Post PCI FFR will be recorded but not disclosed to the operator. The angiographically defined result will be accepted. The patients will have their demographics and procedure details recorded. All patients will receive 3-month telephone follow-up.

Primary Outcome

The primary end-point in this study will be the proportion of patients with a physiologically optimal result post PCI (FFR ≥ 0.90). We hypothesise that our PIOS intervention can increase the proportion of patients achieving this target from 40% to 60% and believe that an increment of at least this magnitude would be necessary to make a future larger study with both patient-oriented clinical (target vessel failure) and health care system (resource utilisation) outcomes acceptable to the interventional cardiology community and potential funders.

Secondary Outcomes

The main secondary outcome measure will centre on assessing change from baseline in self-reported health outcomes at 3 months using both generic and disease-specific quality of life measurement tools.

The EQ5D is a generic quality of life measurement tool which expresses preference for health status using a single index score and is the recommended tool by the National Institute for Health and Clinical Excellence (NICE) for calculation of Quality-Adjusted Life Years. It covers 5 dimensions of health: mobility, self-care, usual activities, pain/discomfort, and anxiety/depression.

The SAQ is a self-administered, disease-specific measure for patients with coronary artery disease that has previously been demonstrated to be valid, reproducible, and sensitive to

clinical change. The SAQ quantifies patients' physical limitations caused by angina, the frequency of and recent changes in their symptoms, their satisfaction with treatment, and the degree to which they perceive their disease to affect their quality of life.

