The rate of target vessel failure and its component features (cardiac death, myocardial infarction, stent thrombosis, unplanned rehospitalisation with target vessel revascularisation) will be analysed at 3 months.

Additional secondary outcomes including procedural/patient safety factors will also be measured. These would include: procedure time, fluoroscopy dose, contrast dose, complications and cost of additional equipment employed (balloons/stents/intra-coronary imaging).

Power calculations

Assuming (as per data from previous studies) that 40% of patients in the control arm have a post PCI FFR ≥ 0.90 and that it is considered clinically relevant if the equivalent percentage in the PIOS treatment arm is at least 60%, we will require a sample size of 130 per group to have 90% power to be able to detect a difference in the population in these proportions at the 5% significance level.

Expected value of results

1. Confirmation that the proposed PIOS protocol significantly increases the proportion of patients obtaining a physiologically optimal post PCI result will demonstrate the feasibility of this strategy and should lead to an increase in post PCI pressure wire usage to achieve physiologically optimal results for patients.
2. The secondary outcome measures, albeit underpowered for clinical outcomes in this study, will hopefully still give a signal that achieving a target post PCI FFR ≥ 0.90 does yield objective benefits for patients. This could then form the basis for a larger phase 3 trial to confirm improved clinical outcomes and cost-effectiveness of FFR targeted PCI

References

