1.6 Sample Size and Power

260 patients will be randomised.

Previous studies suggest that approximately 40% of patients in the control arm will have a post-PCI FFR ≥ 0.90 .(1-5)

This is in keeping with pilot data from our own institution where, among 50 patients who underwent post-PCI FFR assessment, an initial result ≥ 0.90 was achieved in only 16 /50 (32%).

It is hypothesised that the proposed PIOS intervention will increase the proportion of patients with a final post-PCI FFR ≥ 0.90 by approximately 20% compared to the control group. (a relative improvement of at least 50%).

A sample size of 130 patients per group would be required to have 90% power to detect a 20% absolute difference between groups at the 5% significance level.

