1.8.6 Software

Analyses will be carried out using SPSS Statistics, version 25 and R, version 3.4 or above.

2. Analysis

All applicable analyses will be 2-sided and will be performed using a 5% significance level. All confidence intervals presented will be 95% and two-sided.

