For the binary categorical secondary outcomes, the same analysis approach will be used as with the primary outcome. For quantitative secondary outcomes, two sample t-tests and 95% CI will be used, as well as further analyses using regression to investigate whether any of the baseline characteristics affect the outcome. Given the sample size of 130 per group and large number of baseline characteristics, this will be performed by first investigating each characteristic on its own (together with the treatment group). Any variables that are significant here will be added to build a larger model, bearing in mind sample size limitations.

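### Does listing both an adjusted Wald test and Fisher's exact test for the primary outcome, without saying which decides, leave the trial's conclusion open?

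*SAP*

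**What the plan says.** SAP 2.3.1 gives the primary analysis in one sentence: "A test and 95% CI for 2 proportions (adjusted Wald method) will be employed, together Fisher's exact test". SAP 2.3.2 extends this pair to the other yes/no outcomes: "For the binary categorical secondary outcomes, the same analysis approach will be used as with the primary outcome". The opening of SAP section 2 sets the level: "All applicable analyses will be 2-sided and will be performed using a 5% significance level". SAP 1.2 states a single null hypothesis of no difference between the groups, and SAP 1.3 describes a superiority framework. The protocol names no test for the primary outcome.

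On size, SAP 1.6 says "A sample size of 130 patients per group would be required to have 90% power" for a 20-point absolute difference, and the protocol's power section says the same for 40% against 60%. Neither names the test or formula.

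The protocol also comments on how large a gain would matter. Under Primary Outcome the authors write that they "believe that an increment of at least this magnitude would be necessary to make a future larger study" acceptable to the interventional cardiology community and funders. Under Expected value of results they write: "Confirmation that the proposed PIOS protocol significantly increases the proportion of patients obtaining a physiologically optimal post PCI result will demonstrate the feasibility".

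**The concern.** One hypothesis is given two tests, and nothing in either document says which governs if they disagree. Fisher's test is conservative at this sample size, so disagreement is possible, and the choice of headline could then be made after the data are seen. The term adjusted Wald covers more than one variant, and the SAP does not say which is meant. The stated 90% power is reached by one test and narrowly missed by the other. The same pair also serves target vessel failure and procedural complications, where counts may be small.

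A second worry is attached. The protocol says at least a 20-point gain would be needed to justify a larger study, yet elsewhere treats a significant increase as showing feasibility. No text says how the planned interval is to be read against 20 points, so a result that excludes only zero might be presented as establishing the full increment.

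**Working it through.** **Inputs.** Control proportion 0.40 and PIOS proportion 0.60 (Protocol, Power calculations; SAP 1.6 gives the 40% and the 20-point difference). 130 per group, 90% power (SAP 1.6). Two-sided 5% (SAP section 2). Assumption: adjusted Wald means adding one success and one failure to each arm (Agresti-Caffo). Fisher's two-sided p sums all tables no more likely than the one observed.

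**Step 1: the plan's own figure.** Pooled normal formula, no continuity correction:

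n = [1.960·√(2·0.5·0.5) + 1.2816·√(0.4·0.6 + 0.6·0.4)]² / 0.20² = (1.3859 + 0.8879)² / 0.04 = 129.3, so 130 per group.

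The stated size reproduces. With a continuity correction the answer is 140.

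**Step 2: exact power at 130 per arm.** Sum the product of the Binomial(130, 0.4) and Binomial(130, 0.6) probabilities over each test's rejection region.

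| Test | Power at 40% vs 60% | Size at 40% | Size at 50% |
|---|---|---|---|
| Adjusted Wald | 90.8% | 4.98% | 5.43% |
| Fisher's exact | 88.5% | 3.68% | 4.05% |

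Fisher first reaches 90% at 141 per arm (90.3%; 140 gives 89.95%).

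**Step 3: where the tests part.** Over all 131 × 131 = 17,161 possible tables, 214 are significant by adjusted Wald only and none by Fisher only. For a given control count, the gap is never wider than one PIOS patient.

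With 52/130 controls and 68/130 PIOS: adjusted proportions 53/132 = 0.4015 and 69/132 = 0.5227; difference 0.1212; standard error √[(0.4015·0.5985 + 0.5227·0.4773)/132] = 0.0609. The 95% interval is 0.1212 ± 1.960·0.0609, or +0.2 to +24.1 points (p = 0.047). Fisher p = 0.062. At 69/130 both are significant (Fisher p = 0.046).

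The probability of a split is 1.3% at 40/40, 2.3% at 40/60, and at most 5.0%, for a true 52.25% against 40%.

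**Step 4: what an unranked pair costs.** Because no table is significant by Fisher alone, the rule "significant on either" is exactly adjusted Wald. Its type I error is 4.98% at a 40% rate and peaks at 5.4% near 50%. Having Fisher as a second test adds nothing to it.

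**Step 5: does the form of adjustment matter?** Adding 0, 1, z²/4 or 2 successes and failures per arm gives 90.8% power and a threshold of 68 against 52 controls every time. With 2 added, four tables are significant by Fisher only. At a common 5% event rate, size is 3.7% with 1 added and 2.7% with 2 added (Fisher 2.2%). A rare-event example with 1 added is 2 against 9 of 130: interval +0.1 to +10.5 points, Fisher p = 0.060.

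**Step 6: reading the interval against 20 points.** At a true 40% against 60%, the interval excludes 0 but includes 20 in 88% of trials. Its lower limit reaches 20 in 2.4%, and it lies wholly below 20 in 2.5%.

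**The case for a change.** The best case for a change is that pre-specification exists for the borderline result. At 52 against 68 of 130 the plan supports two opposite statements about its only primary hypothesis, and one clause would settle it at no cost in patients or analyses. The 90% power claim is met only if adjusted Wald leads. For rare secondary outcomes the undefined adjustment does alter the test's behaviour.

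Some of this stands. The plan does not name a deciding test, the 52 against 68 example is correct, and a sponsor who adds a clause does no harm. But the rest carries little weight. The power statement is not an error: it follows from a standard formula, and Fisher's shortfall is 90 − 88.5 = 1.5 points. The order and grammar of the sentence put the adjusted Wald test and its interval first, with Fisher alongside. Since both are committed to in advance, leaving one out would be a visible departure. Which test should lead is itself a matter of taste: adjusted Wald matches the interval and the stated power but slightly exceeds 5% at some rates, while Fisher stays near 4%. The rare secondary outcomes do not decide the trial, and the protocol itself calls them underpowered for clinical outcomes.

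On the 20-point reading, the SAP tests a null of no difference under a superiority framework. The protocol's sentence on magnitude records a belief about what others would accept, and the feasibility sentence is narrative. Neither is a success criterion, and neither says that significance would prove a 20-point gain. The interval will be published, so any reader can set it against 20. A formal rule would give the same answer, increase shown but 20 points not established, in 88% of trials even when the true gain is exactly 20.

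**Conclusion.** The concern does not call for a change. The SAP omits a detail, but following it as written gives a sound primary result. Success on either test is adjusted Wald alone, with size close to 5% (at most 5.4%) and 90.8% power at the planned 130 per group. The tests can split only over a strip one patient wide, in 1.3% of trials at 40/40 and 2.3% at 40/60, and a split would appear in the report because both tests are planned. The suggested reading against 20 points would add a criterion that the plan does not need and that this sample size could seldom resolve.

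This rests on the one-success, one-failure form of the adjustment. The power and the 68-patient threshold do not depend on that choice. The statement that Fisher is never significant alone does, though the exception found with two added per arm is only four tables in 17,161. The figures also assume that all 260 patients contribute a final FFR; losses would lower the power of both tests.

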1.5 Blinding

Patients will not be informed of their final coronary physiology results. FFR results will not be displayed on the procedure-room monitor and the physiology interface will only be visible to research staff in the control room. These results will only be disclosed to the operator for patients with initial post-PCI FFR <0.90 who are randomized to receive the optimisation strategy. The rationale for maintaining operator-blinding for all other post-PCI physiology results is to try and minimise the potential Hawthorne effect ('observer effect') the study could have on local PCI practices.

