2.2 Baseline Characteristics

Baseline characteristics will be summarised in the FAS as a whole and by treatment group. The following baseline characteristics will be reported:

- Demographics: age (years), sex (male, female), height, weight, BMI, ethnicity (White or White British, Asian or Asian British: South Asian, Asian or Asian British: Chinese, Asian or Asian British: Other Asian, Black or Black British, Mixed or Multiple, Other)
- Lifestyle Factors: Smoking Status (No, Current, Ex-Smoker <12 months, Ex-Smoker >12 months)
- Vital Sign Observations: heart rate, blood pressure
- Pharmaceutical therapy (medications used for treatment of cardiovascular disorders including primary and secondary therapies)
 - Number of antianginal medications
- Medical History including Risk Factors (yes/no unless otherwise stated)
 - Indication for Angiogram (Stable Angina, ACS-NSTEMI, ACS-Unstable Angina)
 - Time since NSTEMI
 - Troponin Assay Used and Peak Troponin Recorded if NSTEMI
 - Hypertension
 - Hypercholesterolaemia
 - Diabetes
 - TIA/Stroke
 - CKD
 - Thyroid Dysfunction
 - Pacemaker
 - ICD
 - Atrial Fibrillation
 - Heart Failure (No, HF-rEF, HF-pEF)
 - NYHA Class if Heart Failure (1-4)
 - Previous PCI
 - Previous MI
 - History of Previous MI in Target Vessel if Yes
 - CABG
 - Angina
 - Canadian Cardiovascular Society (CCS) Class if Angina (1-4)
 - Valvular Heart Disease
 - Valve Replacement/Repair
 - Family History of CAD
- Health Status questionnaire scores:
 - Seattle Angina Questionnaire
 - EQ-5D-5L
- Procedural Characteristics
 - Vascular Access (Radial, Femoral, Brachial)
 - Sheath Size

- Multivessel Procedure (Yes, No)
- Procedure Time
- Duration of Research Protocol
- Contrast Dose
- Dose Area Product
- Radiation Dose
- Total Duration of Adenosine Infusion
- Total Dose of Adenosine
- Total Number of Stents Deployed in Study Artery
- Total Length of Stents Used in Study Artery
- Diameter of Largest Balloon used for PCI
- Largest Stent Diameter

- Angiographic Characteristics
 - Target Coronary Artery Segment
 - Lesion Severity by Operator's Visual Assessment (Normal, Plaque Disease, <25%, 25-49%, 50-74%, 75-94%, >/= 95%, Subtotal Occlusion, Occluded)
 - AHA Lesion Type
 - Lesion APPROACH Score
 - Gensini Score
 - QCA Lesion Length
 - Pre- and Post-PCI QCA Diameter Stenosis
 - Pre- and Post-PCI QCA Area Stenosis
- Pre- and Post-PCI Coronary Physiology Test Results
 - Ratio of distal coronary to aortic pressure (Pd/Pa)
 - Diastolic Pressure Ratio (dPR)

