 - Resting Full-cycle Ratio (RFR)
 - Mean Resting Transit Time
 - Fractional Flow Reserve (FFR)
 - Mean Hyperaemic Transit Time
 - Coronary Flow Reserve (CFR)
 - Index of Microcirculatory Resistance (IMR)
 - IMR corrected by Yong's Formula (IMRc)
 - Presence of 'Abrupt Drop' pattern on pressurewire pullback assessment
 - Time to Hyperaemia
 - Presence of Pressure Wire Drift >/=0.04 on pullback
 - Requirement for Repeat Assessment due to Drift
 - Chest Discomfort During Adenosine Infusion (None, Slight, Moderate, Severe)
 - Pre-PCI 'Grey Zone' FFR (0.75-0.80) Value (Yes/No)
 - Final FFR ≥0.90 (Yes/No)
 - Final FFR ≥0.80 (Yes/No)

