2.3.2 Secondary Outcomes

- Change from baseline in SAQ and EQ-5D-5L scores at 3 months
- The rate of target vessel failure and its components (cardiac death, myocardial infarction, stent thrombosis, unplanned rehospitalisation with target vessel revascularisation) will be analysed at 3 months
- The proportion of patients with final post-PCI $\text{FFR} \leq 0.80$
- The proportion of patients with final post-PCI $\text{DPR} \geq 0.90$
- The proportion of patients with final post-PCI $\text{RFR} \geq 0.90$
- The proportion of patients with final post-PCI $\text{CFR} \geq 2.0$
- The proportion of patients with final post-PCI $\text{IMR} > 25$
- The proportion of patients with final post-PCI $\text{IMRc} > 25$
- ΔFFR from pre-PCI to final post-PCI value
- ΔDPR from pre-PCI to final post-PCI value
- ΔRFR from pre-PCI to final post-PCI value
- ΔCFR from pre-PCI to final post-PCI value
- $\Delta\text{Resting transit time (TT}_{\text{rest}}\text{)}$ from pre-PCI to final post-PCI value
- $\Delta\text{Hyperaemic transit time (TT}_{\text{hyp}}\text{)}$ from pre-PCI to final post-PCI value
- ΔIMR from pre-PCI to final post-PCI value
- ΔIMRc from pre-PCI to final post-PCI value
- ΔFFR from pre-PCI to final post-PCI value
- Percent FFR change from pre-PCI to final post-PCI value
- Percent DPR change from pre-PCI to final post-PCI value
- Percent RFR change from pre-PCI to final post-PCI value
- Percent CFR change from pre-PCI to final post-PCI value
- Percent TT_{rest} change from pre-PCI to final post-PCI value
- Percent TT_{hyp} change from pre-PCI to final post-PCI value
- Percent IMR change from pre-PCI to final post-PCI value

- Percent IMR_c change from pre-PCI to final post-PCI value
- Procedure Duration
- The cost of additional equipment employed in the experimental arm
- Fluoroscopy Dose
- Contrast Material Dose
- Incidence of procedural complications such as coronary artery dissection or perforation.
- An 'As Treated' analysis of the preceding primary and secondary outcome measures

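### SAP 2.2 lists post-randomisation results, including the primary endpoint itself, as baseline characteristics, and 2.3.1 and 2.3.2 make every baseline characteristic a candidate covariate in the secondary regressions

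*SAP*

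**What the plan says.** The protocol (Methods/Design) randomises patients before PCI is performed. Everything measured during or after PCI is therefore post-randomisation.

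SAP 2.2 nevertheless places the following among the baseline characteristics:

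- procedure time, contrast dose and radiation dose
- "Total Number of Stents Deployed in Study Artery", total stent length and largest balloon
- post-PCI QCA
- a block headed "Pre- and Post-PCI Coronary Physiology Test Results", which ends with "Final FFR ≥0.90 (Yes/No" and "Final FFR ≥0.80 (Yes/No"

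The first of those last two items is the primary endpoint.

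SAP 2.3.1 then sets the covariate rule for the primary outcome: "Additional secondary analyses on this outcome will use logistic regression to investigate whether any of the baseline characteristics affect the outcome". Each characteristic is screened beside treatment group. SAP 2.3.2 repeats the rule for quantitative secondary outcomes and gives binary ones the same treatment as the primary. In both sections the build step is: "Any variables that are significant here will be added to build a larger model, bearing in mind sample size limitations". Several 2.2 items reappear in 2.3.2 as outcomes, for example "Contrast Material Dose".

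**The concern.** The closing phrase about sample size limits how many variables enter a model. It does not say which are eligible, and nothing else in either document restricts candidates to variables fixed before allocation. Two problems follow.

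1. **Circularity.** An outcome can be offered as its own predictor, or as a predictor of something calculated from it.
2. **Conditioning on consequences of allocation.** Stent number, stent length, procedure time and similar items can be changed by the optimisation steps, which apply to Group 1 only. A model containing them no longer tells the reader whether a baseline characteristic affects the outcome, which is the SAP's stated purpose. The treatment coefficient in the same model can also move.

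The second matters more in practice. Such a model fits without any warning, and the SAP's own label makes the variable look legitimate. The study is meant to explain mechanisms of suboptimal FFR and support a phase 3 trial, so a misread stent coefficient could mislead that work.

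**Working it through.** **The plan's own figure.** For 40% v 60%, two-sided 5%, 90% power:

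n = [1.960·√(2·0.5·0.5) + 1.2816·√(0.4·0.6 + 0.6·0.4)]² / 0.20² = (1.3859 + 0.8879)² / 0.04 = 129.3, so 130 per group (power 0.902).

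This reproduces the stated size. The calculation uses no covariates, so the point does not touch it.

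**Overlap between the 2.2 list and the outcomes, read literally**

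| Outcome | Item in 2.2 | Overlap |
|---|---|---|
| Primary, FFR ≥0.90 | Final FFR ≥0.90 | identical |
| Final FFR ≤0.80 | Final FFR ≥0.80 | near-complement (both true only at exactly 0.80) |
| Procedure duration | Procedure time | same |
| Contrast dose | Contrast dose | same |
| Fluoroscopy dose | Radiation dose | same, if they are one measurement |
| Five other dichotomised indices (dPR, RFR, CFR, IMR, IMRc) | Post-PCI value | defining value, if post-PCI means final |
| Eight Δ and eight percent-change outcomes | Pre- and post-PCI values | shared component, if post-PCI means final |

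The condition in the last two rows is needed because the SAP treats initial and final as distinct (1.5 speaks of "initial post-PCI FFR <0.90 who are randomized to receive the optimisation strategy"), while the 2.2 heading says neither. For the Δ outcomes, exact circularity arises only if the pre-PCI and final values are both in the larger model.

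**What a self-regression does.** With 52/130 v 78/130 and the endpoint as its own covariate, separation is complete. The Wald p-value is 0.999. The likelihood-ratio chi-square is −2·260·(0.4 ln 0.4 + 0.6 ln 0.6) = 350. Whether the variable passes the screen depends on a test that the SAP does not name. Either way the failure is obvious.

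**Why stent number is less visible.** Take Group 1 with 40% at or above 0.90 initially: 52 patients reach the target and 78 do not. Under protocol steps B and C, only those 78 can receive an extra stent. Suppose 33% do (26 patients) and the stent has no effect. Then 0 of 26 with the extra stent succeed, against 52 of 104 without it. An inert stent looks harmful because low FFR led to it.

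**With the SAP's own variable.** Model: logit(FFR ≥0.90) on treatment and total stent number, simulated with 130 per arm. Assumptions that are not in the documents: 20% or 40% of patients start with two stents and the rest with one, and s is the share of Group 1 patients below 0.90 who are given an extra stent. In the second scenario the protocol's 40% to 60% holds and every conversion is assumed to come through a stent, so a stented patient converts with probability (0.20/0.60)/s. The unadjusted odds ratio is then (0.6/0.4)/(0.4/0.6) = 2.25.

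| Scenario | s | OR per stent | Treatment OR (unadjusted) |
|---|---|---|---|
| Extra stent has no effect | 33% | about 0.46–0.60 | about 1.12–1.17 (1.0) |
| Extra stent has no effect | 67% | 0.25–0.37 | about 1.5–1.7 (1.0) |
| 40% to 60%, all through stents | 33% | about 1.7–2.1 | about 2.0–2.1 (2.25) |
| 40% to 60%, all through stents | 67% | 0.74–0.79 | about 2.5–2.6 (2.25) |

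At the 5% level stent number passes the screen in about 62–81% of trials in the first row, nearly all in the second, and about 20–27% in the fourth.

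**The case against.** **Status of these models.** They are additional secondary analyses. The treatment effect comes from the two-proportion test, its interval, Fisher's exact test and the t-tests, none of which uses covariates. SAP 2.8 also places the clinical-predictor models for FFR ≥0.90 outside this SAP. All of that stands and limits the importance of the point. A reader might infer that the primary result is compromised; the documents do not support that.

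**Another reading of baseline.** Section 2.2 is a reporting list with its own subheadings, and elsewhere the SAP uses baseline in the ordinary sense, as in change from baseline. If 2.3.1 meant that, no self-regression would arise. This reading is possible but less well supported. Section 2.3.1 refers to the large number of baseline characteristics, and 2.2 is the only list under that name.

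**Overstating the overlap.** A reader might count every Δ and percent-change outcome as circular. That does not follow: screening is one variable at a time, exact circularity for Δ needs two specific values together, and a linear model for percent change is not exact even then.

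**Overstating the stent example.** Comparing Group 1 patients with and without an extra stent gives a starker contrast, but 2.2 lists total stent number, not an extra-stent indicator. Step A also allows post-dilatation or imaging-guided optimisation, so the assumption that all conversions come through stents is an extreme one. At a 67% share under the 40% to 60% scenario, stent number would usually not be selected.

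**Conclusion.** The point holds as a defect in the SAP's covariate rule, limited to the additional secondary regressions. Read literally, which is the better-supported reading, the rule allows self-regression for the primary endpoint, procedure duration and contrast dose, and near-self-regression for final FFR ≤0.80. More cases follow if radiation dose is the fluoroscopy outcome or if post-PCI means final. Those models would fail visibly, so their main cost is a rule that cannot be followed as written and must be narrowed ad hoc.

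The less visible risk is conditioning on what allocation changes. In the settings above the stent-number odds ratio runs from 0.25 to about 2.1, and the treatment odds ratio can move in either direction. These figures rest on an assumed share of extra stents and an assumed starting mix of stents, neither of which is in the documents. They show that the mechanism is real. They do not predict its size or sign in this trial, and it would be wrong to infer that the stent coefficient will be reversed.

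**What to change.** Split SAP 2.2 into two lists and label every post-PCI item initial or final.

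- **List (a):** pre-randomisation and pre-PCI characteristics, plus procedural items that the PIOS steps do not change, such as vascular access and multivessel procedure.
- **List (b):** procedural totals and final post-PCI results that allocation can affect.

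Add to 2.3.1 and 2.3.2: *Candidate covariates come from list (a) only. Neither the outcome nor any component of it other than its pre-PCI or baseline value will be entered.*

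State separately how initial post-PCI values are handled. They are measured before any PIOS step, so allocation to those steps does not change them, but they are not baseline. Initial FFR is also the final FFR, apart from any drift adjustment, for all of Group 2 and for Group 1 patients already at or above 0.90. That is an expected 130 + 0.40·130 = 182 of 260 (70%), or 130 + 0.32·130 = 171.6 of 260 (66%) at the SAP's pilot rate. Keep them out of the baseline-characteristic models and allow them only in separately labelled ones.

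Models that use list (b) to explore mechanisms should be separate, described as associational, and not used to estimate the treatment effect.

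The cost is SAP wording and fewer exploratory models. No new data are needed, and the primary analysis and sample size stay as they are.

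### The secondary regressions screen some 53–62 pre-PCI characteristics one at a time at 5% and keep the winners, so false and overstated predictors are likely; the unadjusted primary test is unaffected

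*SAP*

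**What the plan says.** The primary outcome is compared between arms without covariates, by a two-proportion comparison with an adjusted Wald interval and by Fisher's exact test (SAP 2.3.1). A further step follows: "Additional secondary analyses on this outcome will use logistic regression to investigate whether any of the baseline characteristics affect the outcome". Each characteristic is first fitted alone with treatment, and then: "Any variables that are significant here will be added to build a larger model, bearing in mind sample size limitations".

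SAP 2.3.2 uses the primary-outcome approach for binary secondary outcomes. For quantitative ones it adds regressions to the t-tests, and again "this will be performed by first investigating each characteristic on its own (together with the treatment group".

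No separate screening threshold is given, so the general rule at the start of SAP section 2 is the natural reading: "All applicable analyses will be 2-sided and will be performed using a 5% significance level". No shortlist is named either, so the candidates are the SAP 2.2 list, introduced by "The following baseline characteristics will be reported". The plan sets no limit on model size, multiplicity control, shrinkage or validation.

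Some listed items exist only for part of the sample, for example "NYHA Class if Heart Failure (1-4", "Troponin Assay Used and Peak Troponin Recorded if NSTEMI" and "History of Previous MI in Target Vessel if Yes". Time since NSTEMI and CCS class are of the same kind. SAP 1.8.2 reports counts of missing values but gives no rule for entering missing or not-applicable values in a model.

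**The concern.** The SAP gives the length of the list and the modest sample as its reason for screening one item at a time. Screening does not solve that problem. Every candidate still gets its own 5% test, and the final model then presents the survivors as if they had been chosen beforehand. Three things follow:

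- some retained predictors are noise;
- real predictors are retained mainly when their estimate happens to be large;
- the final p-values and intervals take no account of the search.

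A separate difficulty is that a regression containing an item defined only for some patients drops everyone else, unless not-applicable is given a code.

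At stake is what the trial reports about which patients reach an FFR of 0.90 or more, and about predictors of each secondary outcome. SAP 1.1 says the data could support a later phase 3 study, so a spurious predictor could be carried forward.

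**Working it through.** **1. The plan's own figure.** Inputs from SAP 1.6: 40% in control, a 20-point difference (60%), two-sided 5%, 90% power. With pooled variance and no continuity correction:

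n = [1.960·√(2·0.5·0.5) + 1.282·√(0.4·0.6 + 0.6·0.4)]² / 0.2² = (1.386 + 0.888)² / 0.04 ≈ 129.3, so 130 per group.

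Power at 130 is 90.2%. The sample size reproduces and does not depend on the screening rule.

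**2. Number of candidates.** From SAP 2.2, keeping only items recorded before PCI:

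- demographics 6, smoking 1, vital signs 2, medication 1, history 23, questionnaires 2: total 35;
- plus angiographic 8, physiology indices 9, grey-zone FFR 1: 53 (narrow count);
- plus five other physiology-test items: 58;
- plus troponin counted as two items, and access, sheath size and multivessel procedure: 62 (wide count).

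This restriction favours the plan. The full list has about 74 entries, some of them procedural or post-PCI.

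**3. False selections.** For k independent candidates, all null, the expected number is 0.05k and P(at least one) = 1 − 0.95^k.

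| k | Expected | P(at least one) |
|---|---|---|
| 20 | 1.00 | 64% |
| 30 | 1.50 | 79% |
| 40 | 2.00 | 87% |
| 53 | 2.65 | 93.4% |
| 55 | 2.75 | 94.0% |
| 62 | 3.10 | 95.8% |

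For k = 55, P(two or more) is 76.8%.

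**4. Allowing for correlation.** Simulated score tests adjusted for treatment (n = 260, 40% vs 60%, 55 nulls, 4,000 trials per setting) gave P(at least one):

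- independent: 94.6%;
- four correlated blocks (9, 8, 4 and 6 items, correlation 0.3 to 0.9) plus 28 independent items: 93% down to 84%;
- eleven blocks of five (correlation 0.5 to 0.9): 89% down to 70%.

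The expected number stayed near 2.75 throughout.

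**5. What reaches the final model.** In 400 simulated trials with 55 independent nulls, a mean of 2.58 were selected, at least one in 93%, and at least one was still significant after joint refitting in 92%. With 30 nulls the figures were 1.45, 79% and 78%. The joint model removes almost none of the noise.

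**6. Overstatement of real effects.** Take a true odds ratio of 1.30 per SD. Log OR = 0.262; SE ≈ 1/√(260·0.24) = 0.127; z ≈ 2.07. P(selected) ≈ Φ(2.07 − 1.96) ≈ 0.54. The mean log OR when selected is about 0.262 + 0.127·0.73 ≈ 0.354, an odds ratio of about 1.42. Simulation (3,000 trials) gave 53% and 1.44. The same predictor is therefore missed in nearly half of trials.

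**7. Repetition.** SAP 2.3.2 lists about 22 distinct quantitative outcomes: 2 questionnaires, 8 absolute changes, 8 percentage changes and 4 procedural measures. With 30 to 55 null candidates each, false selections total about 22·1.5 = 33 to 22·2.75 ≈ 60, before the as-treated repeats.

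**8. Subset items.** Prevalences are assumptions, as the documents give none. Complete cases with NYHA class: 260·0.05 = 13, 260·0.10 = 26 or 260·0.20 = 52. With troponin, at 20–40% NSTEMI: 52 to 104. With both, if independent: about 3 to 21.

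**9. Model size available.** Expected successes are 130·0.4 + 130·0.6 = 130, with 130 failures. At ten events per parameter (a working rule, not in the documents), about 13 parameters can be supported.

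**The case against.** **These are secondary explorations.** The regressions look for predictors, while the comparisons between arms are unadjusted. This stands in full. A reader might infer that the primary result, its power or the treatment estimate is compromised; SAP 2.3.1 does not support that.

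**The 94% is a worst case.** This also stands. The list is visibly correlated: height, weight and BMI; Pd/Pa, dPR and RFR; FFR and grey-zone FFR; IMR, IMRc and hyperaemic transit time. Some items will be real predictors. Rare yes/no items hardly ever reach significance: simulated false selection was 0.0%, 0.3% and 1.2% at assumed prevalences of 1%, 2% and 3%. To say that a false predictor is almost guaranteed therefore goes too far. Even so, the chance stayed above one half in every setting run, and correlation alone does not lower the expected number.

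**The plan recognises the problem.** Only in part. The sample-size clause sets no limit an analyst could apply, and it acts after the selection has happened.

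**Shrinkage to a handful of patients is improbable.** Largely right. A reader might infer that the model will end up with 13 to 26 patients. For that, NYHA class must first be significant within those same patients; under the null, simulation gave 0.1% at n = 13 and 3.2% at n = 26 (assumed class distribution). If all five conditional items had full 5% size and were independent, at least one would enter in 1 − 0.95⁵ ≈ 23% of trials, usually one covering more patients. CCS class may exclude few, since stable angina is a main indication. Complete-case fitting is also needed, which the SAP neither states nor excludes.

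**Labelling the screen exploratory would be enough.** It would temper the claims, but the final p-values and intervals would still ignore the selection.

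**Conclusion.** The concern holds for the secondary regressions and should be corrected. For each outcome, about 2.75 false selections are expected if 55 candidates are all null. The chance of at least one is about 94% if they are also independent, and roughly 64–93% with correlation or with only 20 to 40 nulls. Correlation and fewer nulls were examined separately; together, or with many rare items, the chance would be lower. Selected effects are inflated (1.30 reported as about 1.44 in the example), and the final inference takes no account of the search. These figures take the screening level to be the SAP's general 5% and the candidates to be the pre-PCI part of SAP 2.2.

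Loss of patients through conditional items is a lesser risk. It is a gap in the rules, not an expected result. The primary comparison and the sample size are unaffected.

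**What to change.** Replace the screening sentences in SAP 2.3.1 and 2.3.2 with a model specified in advance and fitted once, with no selection by significance.

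- **Primary outcome:** treatment (1), age (1), sex (1), acute coronary syndrome (1), current smoking vs not (1), diabetes (1), target vessel in three levels (2), pre-PCI FFR (1), QCA lesion length (1). That is 10 parameters, or 13 expected successes and 13 failures for each. The six subgroup variables are those in SAP 2.7.
- **Quantitative change outcomes:** the same set plus the outcome's own baseline value, such as baseline SAQ or EQ-5D-5L. For change in FFR that value is already in the set.
- **Binary outcomes with few events** (target vessel failure and its components, complications): the unadjusted comparison only, or a model reduced to match the events.
- **Conditional items:** give them a not-applicable category or leave them out.
- **Other characteristics:** report one-at-a-time associations as estimates labelled exploratory, without selection by p-value. SAP 2.8 already places clinical-predictor analyses outside this plan.

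The cost is SAP wording and somewhat less programming. The real price is that covariates must be chosen before the data are seen, and predictors outside the set will not be formally tested.
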